PROMIS instrumental and emotional health short forms	SA			X			X				(-) 1 / (+) 3 weeks
Addiction treatment and harm reduction program utilization	SA			X			X		X		(-) 1 / (+) 3 weeks
Urine Drug Screen	RA			X			X		X		(-) 1 / (+) 3 weeks
Assessment of blinding	RA						X		X		N/A
Study Administration											
Inventory – Supplies Form	RA									X	N/A
Recruitment Log	RA									X	N/A
Missed Visit and Visit Documentation Form	RA			X		X	X	X	X		(-) 1 / (+) 3 weeks
Monthly Survey Link	RA									X	N/A
Progress Note Checklist ⁴	RA									X	N/A
Protocol Deviation	RA									X	N/A
Visit Compensation Log ⁵	RA									X	N/A
RA Recorded ED visits and hospitalizations	RA									X	N/A
Mental Health Follow-Up Assessment	RA									X	N/A
Study Completion Form	RA									X	N/A
Death Form	RA									X	N/A

¹ Assessment completed within the prescreener survey but is considered a baseline assessment if the participant screens eligible and is enrolled into the study.

² Adapted COMM provided to individuals receiving any opioid therapy in the past 6 months.

³ RA – Research Assistant or Research Coordinator Administered; SA – Self Administered++ = Not captured in eClinical

* = Completed as part of pre-screening for study eligibility

** = May be done after the baseline visit, if there is not enough time to complete before.

*** = Survey is only given to patients who have an integrated PCP and baseline visit

Note – TLFB at 3 and 6 months cannot be completed earlier than or on the target visit date.

Note – All participant-facing documents will be reviewed/approved by the IRB. Minor edits may be made to assessments (e.g., grammar, punctuation, directions, system programming, etc.) as needed. Assessments will only be submitted for re-review if information to be collected is changed (e.g., addition of new questions.).

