11.4.4 Current Opioid Misuse Measure (COMM)

The COMM is a 17-item self-administered questionnaire that is widely used to monitor pain patients receiving opioid therapy.[43, 44] The COMM is designed to detect aberrant behavior associated with misuse of opioid medications, and has been validated in approximately 500 chronic pain patients receiving opioid therapy. We will be adapting the COMM to include an instruction line at the beginning of the survey and before items 9, 14, 15, and 16 to clarify the questions are asking about opioid pain medications. Because the COMM is only intended for use

in individuals who are taking prescription opioids, in our study it will be administered only to individuals who self-report being prescribed opioid medications.

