11.5 Measures of Primary and Secondary Outcomes

11.5.1 Days of Opioid Use (Healthy Living Monthly Survey)

The primary outcome of days of risky opioid use will be measured at baseline and every 30 days using items based on the Addiction Severity Index [40,41] and the COMM: "During the past 30 days, on how many days did you use [drug name]?" The question will be asked separately for heroin/illicit opioids and for nonmedical use of prescribed opioids. For patients with a current opioid prescription, items from the COMM will also be asked. To inform the primary outcome: a) "During the PAST 30 DAYS, on how many days did you need to take pain medications belonging to someone else?" and b) "During the PAST 30 DAYS, on how many days have you had to take more of your medication than prescribed?" The extent of overlap between these different types of risky use will also be measured, when applicable. The number of days of risky use for an individual will be the sum of days for each of these questions minus the overlap. Overlap between illicit use and nonmedical use will be calculated so that every individual will have a calculated number of days of risky use. To inform secondary outcomes, the following items, adapted from the COMM, will also be administered: c) "During the PAST 30 DAYS, on how many days did you borrow pain medication from someone else?" and d) "During the PAST 30 DAYS, on how many days did you use your pain medication for symptoms other than for pain (e.g., to help you sleep, improve your mood, or relieve stress)?". The assessment is self-administered using a computerized form. This approach to measuring days of drug use was used for assessing the primary outcome in the QUIT trial, where it demonstrated feasibility and sensitivity to change, including for opioid use.[21]

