2.2.3 Exploratory Objectives

Exploratory Objective 1 is to assess the impact of STOP on patient participants' engagement in primary care. There is potential for the intervention to disrupt the patient-PCP relationship, particularly if it leads to a dose reduction or cessation of opioid prescribing by the PCP. In the Transforming Opioid Prescribing in Primary Care (TOPCARE) study [1], a post-hoc analysis indicated that patients in the intervention arm whose opioids were discontinued were less likely to follow up with their PCP. We believe that the multicomponent STOP intervention, which also includes telephone health coaches and PCP brief advice to support patient participants in reducing their opioid use, will not lead to decreased primary care engagement. However, this could be an important unintended consequence of the intervention. We will assess primary care engagement by measuring the frequency of kept appointments and missed appointments in each arm.

Exploratory Objective 2 is to examine the time to development of moderate-severe OUD or opioid-related overdose for patient participants in both treatment conditions. We anticipate a low rate of these events in our 12-month trial. However, given the lack of knowledge regarding opioid use trajectories among individuals with subthreshold OUD, our study may contribute valuable descriptive data to inform future interventions.

Exploratory Objective 3 is to measure the rate of fatal opioid-related overdose deaths. We anticipate very low rates, and potentially no overdose deaths, during the 12-month trial. However, given the importance of this outcome, it will be measured for participants in both treatment conditions. Where information about cause of death is available, we will seek to identify opioid-related overdose deaths, other substance overdose deaths, and other causes of death.

Exploratory Objective 4 is to examine the receipt of addiction treatment (including MOUD) and harm reduction services. Individuals with subthreshold OUD (as opposed to those with moderate-severe OUD) are expected to have little or no involvement with addiction services, but some participants (particularly those who develop moderate-severe OUD during the course of the study or have a co-occurring non-opioid substance use disorder) may utilize such services. Through the involvement of telephone health coaches and a NCM that can recommend and facilitate

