7.2 Analysis of the Primary Outcome Measure

7.2.1 Calculation of the Number of Days of Risky Opioid Use for the Primary Outcome

Days of risky opioid use as measured in the Healthy Living Monthly Survey (HLM) will be used for the primary outcome analysis. No other data source, including Timeline Followback (T01), will be incorporated into the primary outcome analysis. The decision rule for generating the number of days of risky opioid use (illicit opioid use and nonmedical opioid use) during the past 30 days is to add up the days of different kinds of risky opioid use (e.g., use own prescription opioid medications more than prescribed, use opioid medications belonging to someone else, etc.), and then subtract the days when the risky opioid use was counted multiple times due to overlap (e.g., using heroin or fentanyl on the same day as using prescription opioids more than prescribed should only count as one day). The days of different kinds of risky opioid use are collected in the following questions:

For patient participants that report they currently have a prescription for an opioid pain medication (HMOPIRX=1):

- a) (HMPNKOTH) During these 30 DAYS, on how many days did you need to take pain medications **belonging to someone else?** (Enter "0" for never);
- b) (HMRXMORE) During these 30 DAYS, on how many days did you have to **take more of your medication than prescribed?** (Enter "0" for never);

For patient participants that do not report currently having a prescription for an opioid pain medication (HMOPIRX=0):

- c) (HMOPINP) During these 30 DAYS, on how many days did you use **prescription opioid medications** that were not prescribed to you? (Enter "0" for never)

For all patient participants:

d) (HMHERFYL) During these 30 DAYS, on how many days did you use **heroin or fentanyl?** (Enter "0" for never)

The days of overlap are collected in the following questions:

For patient participants that report currently having a prescription for an opioid pain medication (HMOPIRX=1) and reported > 0 days for both HMPKOTH and HMRXMORE:

e) (HMPOSDNY) During these 30 DAYS, did you ever use your own prescription opioid medications more than prescribed **on the same day** that you used opioid medications that belonged to someone else? (y/n);

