7.7 Definition of Secondary Outcome Measures

Measures of Patient-Level Outcomes

1. Days of substance use: Self-reported days of substance use are collected at baseline and once every 30 days. Patient participants are asked to specify the number of days of use in the past 30 days (range is 0-30 days, value=0 for substances that were not used). For

binge alcohol use, the measure defines the cutoff as 5+ drinks (for men under age 65), and 4+ drinks (for women and men age 65 and over). Measures of substance use are calculated as the sum of consecutive assessments of days of use in the past 30 days. For example, days of use in the past 90 days is calculated as the sum of three consecutive assessments of days of use in the past 30 days.

- a. H2.1. Days of binge alcohol use:
 - i. In the past 30 days, measured at baseline and monthly for 12 months.
 - ii. In the past 90 days, assessed at 3, 6, 9, and 12 months.
 - iii. In the past 180 days, assessed at 6 and 12 months.
- b. H2.2. Days of benzodiazepine use:
 - i. In the past 30 days, measured at baseline and monthly for 12 months.
 - ii. In the past 90 days, assessed at 3, 6, 9, and 12 months.
 - iii. In the past 180 days, assessed at 6 and 12 months.
- c. H2.3. Days of stimulant drug use (cocaine and amphetamine-type stimulants):
 - i. In the past 30 days, measured at baseline and monthly for 12 months.
 - ii. In the past 90 days, assessed at 3, 6, 9, and 12 months.
 - iii. In the past 180 days, assessed at 6 and 12 months.
- d. H2.4. Days of marijuana use.
 - i. In the past 30 days, measured at baseline and monthly for 12 months.
 - ii. In the past 90 days, assessed at 3, 6, 9, and 12 months.
 - iii. In the past 180 days, assessed at 6 and 12 months.
- e. H2.5. Days of other drug use (not including opioids, benzodiazepines, stimulants and marijuana).
 - i. In the past 30 days, measured at 3, 6, 9, and 12 months.
- f. H2.6. Increase in number of days of risky opioid use from baseline to follow-up at 6 and 12 months:
 - i. Days of opioid use in the past 30 days, measured at baseline and monthly for 12 months.
 - ii. Days of opioid use in the past 180 days, assessed at 6 and 12 months.
- g. H2.7. Prescription opioid misuse behaviors, among participants receiving prescribed opioids:
 - i. Days of taking prescribed opioids for symptoms other than for pain, using prescribed opioids more than prescribed, or taking pain medication belonging to someone else, measured at baseline and monthly for 12 months.

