This table will be repeated by visit and prescription for opioids in the past 6 months (yes/no) as reported on the COMM. The table will present the number and percentage of participants at that visit that reported having an opioid prescription in the past 6 months. If a patient participant does not complete the COMM assessment at that visit, the previous COMM response will be used to determine if the patient participant has an opioid prescription. For example, if the patient participant does not do the 12-month COMM assessment but has a 12-month UDS, the COMM response from the 6-month visit will be used to categorize the participant at the 12-month visit. If

the patient participant does not have any COMM responses from the baseline, 6 or 12-month visits but has UDS collected for those visits, it will be assumed the patient participant does not have an opioid prescription for any of the visits.

The following analysis will be done by the LN:

The proportions of individuals whose average number of days (within 30 days) of illicit or nonmedical opioid use during 180 days of follow-up increased relative to their baseline measure (days of use in the 30 days before the baseline assessment, H2.6) will be compared between groups at 6 months and 12 months using chi-square test respectively.

Descriptive summary statistics for COMM score assessed at screening and at 6 and 12 months (H2.7 h), Comparisons of the secondary outcomes between the two treatment arms will be conducted using t-tests or Mann-Whitney tests for continuous measures, chi-square tests for categorical measures.

Generalized estimating equations (GEE) to account for correlation of responses within PCP cluster will be fit for the incidence of moderate to severe OUD (defined as a score of at least 4 on the CIDI, H2.8) and drug use disorder (PDSQ drug items, H2.9) and alcohol use disorder (PDSQ alcohol items, H2.9) assessed at 6 and 12 months separately. Treatment effect is estimated adjusting for baseline level of each measurement. Time trend is evaluated using a time variable.

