Self-reported overdose risk behavior will be measured by the overdose risk behavior questionnaire (which gives a numeric score) at baseline, 6, and 12 months. Mean scores will be compared between groups at 6 and 12 months in a random-effect regression model. Also, the total number of non-fatal opioid-related overdose events in the past 3 months will be measured at baseline, 6, and 12 months. Mean numbers of opioid-related overdose events will be compared between groups in a random-effect regression model (H 2.10).

Changes in pain-related symptoms and functioning from baseline as measured by the BPI (which calculates a numeric score) will be compared between treatment arms using Mann-Whitney tests. As the scientific goal is to demonstrate no worsening of pain, a noninferiority test will compare changes in BPI score between treatment and control groups with a minimal clinically important difference of 1 based on the IMMPACT recommendations. A secondary analysis will distinguish the effect of STOP on the change in pain-related symptoms for participants with opioid prescriptions at baseline, and the effect for those who were enrolled solely due to illicit use.

Symptoms of depression, suicidality, anxiety (H2.12), and poor sleep (H2.13) in the past two weeks will be measured at baseline and quarterly (PHQ-8) and at baseline, 6, and 12 months (PROMIS anxiety and sleep measures and PSS). Mean values will be compared between treatment arms in random-effect regression models.

Health-related quality of life (H2.14), and ED and hospital utilization (H2.15) in the past two weeks will be measured at baseline and at 6 and 12 months. Mean values will be compared between treatment arms in random-effect regression models.

Similar models will be fit for the Aim 3 objectives, but these will use provider rather than patient as the unit of observation, so will not need a PCP effect to adjust for within-PCP correlation. Regression models will be used to compare number of prescriptions of high-dose opioids within 12 months of follow-up between treatment arms as well as number of days prescribed during 12 months follow-up. Similar analyses will be done for number of prescriptions for any opioids or benzodiazepines, numbers of naloxone kits prescribed, numbers of urine toxicology tests ordered and completed, and number of patient participants receiving a new diagnosis of OUD.

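### H2.7 has no baseline-defined analysis set: its data depend on prescription status after randomisation, which STOP is expected to change

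*SAP*

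**What the plan says.** SAP 7.7 states H2.7 as "Prescription opioid misuse behaviors, among participants receiving prescribed opioids". Its components are monthly day counts (use for reasons other than pain, use above the prescribed amount, use of another person's pain medication) and the COMM score at screening, month 6 and month 12. No time point is attached to the prescription status.

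The instruments carry their own gates:

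- **Monthly survey.** Protocol 11.5.1: "For patients with a current opioid prescription, items from the COMM will also be asked". SAP 7.2.1 applies the same gate through HMOPIRX. Patients without a current prescription get a different item, HMOPINP, on use of prescription opioids not prescribed to them. H2.7 does not name HMOPINP.
- **COMM.** Protocol 11.4.4 says "it will be administered only to individuals who self-report being prescribed opioid medications". The footnote to Protocol Table 6 says "Adapted COMM provided to individuals receiving any opioid therapy in the past 6 months". These are not the same rule.

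SAP 7.8 compares arms with t-tests or Mann-Whitney tests. It rules out multiple imputation for secondary outcomes; that sentence sits in the H2.1-H2.5 text but is worded generally. Nothing covers patients who leave or join the prescribed group after baseline. By contrast, the secondary pain analysis in the same section is anchored "for participants with opioid prescriptions at baseline".

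**The concern.** Prescribing is something the intervention is meant to move. Protocol 2.1 expects lower prescribing of high-dose and of any chronic opioids under STOP. SAP 2.2.3 notes that STOP may disturb the patient-PCP relationship, "particularly if it leads to a dose reduction or cessation of opioid prescribing by the PCP". Protocol 4.1 cites a parent trial with more dose reduction or discontinuation in the intervention arm (AOR 1.6).

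H2.7 therefore conditions on a post-randomisation status that may differ by arm. Stopping could also be tied to misuse, and more closely in STOP. Under Protocol 10.6.2, STOP PCPs receive a summary of the screening results, and the nurse conducts urine tests and pill counts for patients on chronic opioids and reviews high-risk patients with the PCP. EUC PCPs work without the nurse. If heavier misusers are taken off opioids more often in STOP, the mean among those remaining falls without any change in behaviour. Use of non-prescribed opioids by patients taken off would not appear in H2.7.

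**Working it through.** The documents give no sample size, power or expected effect for H2.7, so there is no planned figure to reproduce.

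**1. Who drops out of which comparison** (COMM gate as in Table 6)

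| Component | Stopped in months 1-6, no later prescription | Stopped in months 7-12 |
|---|---|---|
| Monthly items | lost from the first month without a prescription | lost from the first month without a prescription |
| COMM, month 6 | largely kept: therapy since baseline falls in the look-back | not affected |
| COMM, month 12 | lost | kept |

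Reading the H2.7 group as prescribed at baseline does not by itself cure this, because the gated items are not asked once the prescription ends.

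**2. Size of the group.** Protocol 8.2.2 expects 15-20% of about 300 patients: 0.15 × 300 = 45 and 0.20 × 300 = 60, or 22.5-30 per arm.

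**3. Shift with similar selection in both arms.** All inputs here are assumptions. COMM is gamma with mean 12 and SD 8, the same in both arms, with no treatment effect. The probability of stopping is logistic in COMM. STOP multiplies the odds of stopping by 1.6, borrowing the parent trial's composite AOR. Difference in means (STOP minus EUC) among those remaining, in COMM points:

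| EUC stopping | OR 1.0 per SD of COMM | OR 1.5 | OR 2 | OR 3 |
|---|---|---|---|---|
| 10% | 0 | -0.17 | -0.25 | -0.30 |
| 20% | 0 | -0.24 | -0.34 | -0.39 |
| 30% | 0 | -0.27 | -0.37 | -0.42 |

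In SD units: 0.17/8 = 0.02 to 0.42/8 = 0.05. The standard error of the difference with nobody removed is 8 × √(2/30) = 2.07 to 8 × √(2/22.5) = 2.39 points, so the largest shift is 0.42/2.07 = 0.20 standard errors. With a stopping OR of 1.2 instead of 1.6, the shift is 0.06-0.16 points.

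**4. When it grows.** A second illustration uses standard normal misuse scores, log-odds of being off opioids rising by b = 0.5 to 2 per SD in both arms, and a two-sided 5% test with clustering ignored. For an OR of 1.6, an EUC rate of 10% gives odds 0.111 × 1.6 = 0.178, or 15% in STOP; 20% gives 0.25 × 1.6 = 0.40, or 29%.

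| Off opioids, EUC / STOP | Shift (SD) | Chance of a false result favouring STOP (nominal 2.5%) |
|---|---|---|
| 10% / 15% and 20% / 29% | -0.02 to -0.10 | 3.0-5.7% |
| 10% / 30% | -0.09 to -0.23 | 4.7-14.7% |
| 5% / 40% | -0.17 to -0.41 | 7-35% |

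At b = 0 the shift is zero and the chance stays at 2.5%. The first row reaches further than step 3 because b = 2 is a steep gradient (odds ratio 7.4 per SD) and the scores are normal, not skewed.

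If only STOP selects on misuse, the step 3 model at its mildest setting (10% EUC stopping, OR 1.5 per SD) gives -0.56 points, or 0.56/8 = 0.07 SD.

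**The case against.** The case against acting is substantial, and much of it stands.

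- **The AOR of 1.6 is not a stopping odds ratio.** It covers dose reduction or discontinuation together, and dose-reduced patients stay in H2.7. This stands; 1.6 is an illustrative input.
- **The direction is not documented.** No passage says heavier misusers are the ones stopped. The bias vanishes if stopping is unrelated to misuse or if the arms stop alike with the same selection, and it reverses if lighter misusers are stopped. This stands.
- **The loss is partial.** The look-back protects most of month-6 COMM. The gate is also patient self-report and covers prescriptions from any provider, so the group is not simply those the study PCP kept on opioids. This stands, though the month-6 protection depends on the Table 6 rule and not on a narrower reading of Protocol 11.4.4.
- **Some of the diagnostic exists.** SAP Table 64 shows past-6-month prescription status by visit and arm, and H3.1 covers any opioid prescriptions. This helps, but Table 64 counts all participants, not those prescribed at prescreening, and fills a missing COMM with the previous response.

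A reader might infer that the urine table has the same fault, since "This table will be repeated by visit and prescription for opioids in the past 6 months (yes/no) as reported on the COMM". It does not. That table is descriptive and serves to verify self-report; interpreting a month-12 positive needs prescription status near month 12.

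What remains is that neither document defines the H2.7 set, and the monthly items and month-12 COMM depend on a status the intervention is expected to alter.

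**Conclusion.** The defect is real but limited. H2.7 lacks a baseline-defined set, and its monthly items and month-12 COMM are gated on prescription status after randomisation. Bias toward STOP requires that those stopped misuse more and that the arms differ in stopping or in selection. With similar selection and an assumed stopping OR of 1.6, the shift is about 0.02-0.05 SD. It becomes material only with a strong arm difference, such as 5% against 40% off opioids. The stopping rates, selection strength, COMM mean and COMM SD are assumptions, and the illustrations do not model the skewed monthly day counts.

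Two stronger readings are not supported. The first is that the trial as a whole could show less misuse with no change in behaviour. The primary outcome asks every patient about risky use and still counts non-prescribed use after a prescription ends; H2.7 is one secondary outcome, in about 45-60 patients, without multiplicity adjustment. The second is that the bias is a large fraction of the expected effect. The documents state no expected effect for H2.7, and a benchmark built from an emergency-department trial's percentage reductions (50% against 39.5%) would rest on the assumed COMM mean.

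**What to change.** In SAP 7.7 and 7.8:

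1. Define the H2.7 set as participants reporting an opioid prescription in the past 6 months at prescreening, which SAP Table 18 already tabulates. Analyse by assigned arm whatever their later prescription status.
2. For monthly days of using another person's medication, use HMOPINP in months with no current prescription. Its wording differs slightly from the gated item, so say so.
3. Report own-medication misuse days separately, with 0 in months without a prescription labelled as reflecting the absence of a prescription. Otherwise STOP is credited with behaviour change for a prescribing change.
4. Show the share of the set still prescribed, by arm and time point.
5. Report month-12 COMM as observed-only, labelled as conditional on a recent prescription. Keep any imputed version as a sensitivity analysis, because Protocol 11.4.4 does not intend the COMM for people not taking prescription opioids.
6. Reconcile the COMM gate in Protocol 11.4.4 with the footnote to Table 6.
7. Leave the urine table split by visit-level prescription status.

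The cost is SAP wording and light programming on data already collected. The price is a composite scoring rule for months without a prescription, which needs a clear label. If any H2.7 results are already known, mark the change as post hoc, as SAP section 14 does for the zero-inflated model.
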